8.2 Study flow chart

Figure 1 Schematic of the study design (PBMC-only subjects)

Group design (PBMC-only subjects)

[figure not shown]

* The follow-up visit will be 9–11 days after a subject's last dose (Days 23–25).

Subject fasting requirements are detailed in section 11

Figure 2 Schematic of the study design (PET subjects)

Group design (PET subjects)

* 1 subject in Group 1 will have imaging session 3 on Day 22, and 1 subject in Group 2 will have imaging session 3 on Day 23.

† The follow-up visit will be 9–11 days after a subject's last dose (Days 23–25) or 2–4 days after imaging session 3, whichever is later.

Subject fasting requirements are detailed in section 11

8.3 Definition of the end of the trial

The end of the trial is defined as the final follow-up visit by the last subject. If the trial is terminated prematurely, the trial ends when the sponsor notifies the investigator in writing that the trial has finished, or when the last subject attends the final follow-up visit, whichever is later.

8.4 Stopping criteria

8.4.1 *Trial stopping criteria*

The trial will be stopped if either of the following occurs:

- 1 or more SAEs considered to be at least possibly related to study treatment; or
- 2 or more severe or clinically significant AEs considered to be at least possibly related to study treatment at any dose level.

If, after an internal safety review, it is appropriate to restart the trial, a substantial amendment will be submitted to the MHRA and research ethics committee (REC). The trial will not restart until the amendment has been approved by the MHRA and REC.

8.5 Criteria for proceeding to Group 2

8.5.1 *Review of data by the Safety Review Group*

Before proceeding to Group 2, the SRG will review the safety, tolerability and PK data from Group 1. The SRG will include (as a minimum) the principal investigator (or medically qualified delegate) and the sponsor's medically qualified representatives (Primary Medical Officer and the Head of Translational Medicine [or delegate]). Each dose decision will be made and documented in line with HMR SOPs. All data used to support dose selection will be quality checked.

The SRG will review safety, tolerability, and PK data up to 6 days after the final dose (Day 20) from all subjects dosed in Group 1. In the event of a subject withdrawal prior to Day 20, all available safety, tolerability, and PK data from that subject will be included in the SRG review. The review will include (as a minimum) data from at least 4 evaluable subjects. An evaluable subject is one who completes dosing and has undergone procedures until 6 days after final dosing (Day 20), and had no major protocol deviations.

The data reviewed will include, as a minimum:

- AEs and SAEs, including description, frequency, intensity, onset, duration, and relationship to treatment
- vital signs

- 12-lead safety ECG
- laboratory safety tests
- PK parameters

Group 2 will proceed only if the following are true.

- The safety and tolerability of [REDACTED] ASN51 QD are deemed acceptable
- In any individual subject, C_{max} and AUC_{24} after [REDACTED] ASN51 QD are predicted not to exceed the following limits, which are based on the NOAEL in 4-week toxicology in dogs (as detailed in sections 6.2.1).

C_{max} : 3,000 ng/mL	AUC_{24} : 25,000 ng·h/mL
-------------------------	-----------------------------

The trial will be stopped if any of the criteria in section 8.4.1 are met.

9 Trial population

9.1 Planned number of subjects

Up to 12 healthy volunteers, excluding replacements

9.2 Inclusion criteria

The inclusion criteria detailed below should be used to determine eligibility at screening only (unless otherwise specified).

1. Male healthy volunteers (PET subjects); or healthy males or females of non-childbearing potential (PBMC-only subjects). A woman is considered to be of non-childbearing potential if she meets one of the following criteria:
 - post-menopausal (amenorrhea for at least 12 months, and follicle-stimulating hormone (FSH) at screening confirms post-menopausal status)
 - has no uterus, ovaries or fallopian tubes
2. Aged 25–55 years.
3. Deemed healthy based on medical history, physical examination, ECG, vital signs, neurological examination, and laboratory tests of blood and urine.
4. Body weight ≥ 50.0 kg (men) or ≥ 45.0 kg (women).
5. Body mass index (BMI; Quetelet index) in the range 18.0–30.9 kg/m² (inclusive).

$$\text{Body Mass Index} = \frac{\text{weight [kg]}}{(\text{height [m]})^2}$$

6. Sufficient intelligence to understand the nature of the trial and any hazards of participating in it. Ability to communicate satisfactorily with the investigator

and to participate in, and comply with the requirements of, the entire trial (ie be fluent in the local language).

7. Willingness to give written consent to participate after reading the ICF, and after having the opportunity to discuss the trial with the investigator or their delegate.
8. Agree to follow the contraception requirements of the trial as described in section 11.
9. Agree not to donate blood or blood products during the study and for up to 3 months after the final visit.
10. Willingness to give written consent to have data entered into The Overvolunteering Prevention System (TOPS).
11. Agree not to post any personal medical data or information related to the study on any website or social media site (eg Facebook, Twitter, etc) until the trial has ended.

9.3 Exclusion criteria

The exclusion criteria detailed below should be used to determine eligibility at screening only (unless otherwise specified).

1. Clinically relevant abnormal medical history, physical or neurological findings, ECG, or laboratory values at screening, or before the baseline PET scan (PET subjects only), or before the first dose of trial medication, that could interfere with the objectives of the trial or the safety of the volunteer.
2. History or presence of acute or chronic illness, or clinically-significant medical abnormality, sufficient to invalidate the volunteer's participation in the trial or make it unnecessarily hazardous.
3. History or presence of any disease, medical condition, or surgery (eg stomach bypass), likely to affect the absorption, distribution, metabolism, or excretion of medicines. Subjects with a history of cholecystectomy should be excluded.
4. Impaired endocrine, thyroid, hepatic, respiratory or renal function, diabetes mellitus, coronary heart disease, or history of any psychotic mental illness.
5. Presence or history of severe or clinically significant adverse reaction to any drug; or a history of sensitivity to ASN51 (all subjects) or the PET radioligand, [¹⁸F]-IMA601 (PET subjects only), or any components of those medications.
6. History of psychiatric disorders, including substance use disorders, according to the Diagnostic and Statistical Manual of Mental Disorders, 5th Edition (DSM-5) criteria.
7. Any diagnosis of intellectual disability (intellectual developmental disorder) or mental retardation.

8. History of epilepsy or seizures, other than a single instance of benign febrile convulsion in childhood.
9. History of clinically significant head trauma, including closed head injury with loss of consciousness.
10. History of symptomatic orthostatic hypotension (ie postural syncope).
11. History of neuroleptic malignant syndrome.
12. History of chronic urinary tract infections.
13. Significant suicide risk as assessed by C-SSRS.
14. Frequent use (≥ 3 days a week) of any nicotine-containing product (eg cigar, cigarette, or snuff; or any product used for smoking cessation [eg nicotine gum or plasters]) within 3 months before the baseline PET scan (PET subjects) or first dose of trial medication (PBMC subjects).
Use of any nicotine-containing product is prohibited from within 1 week of the baseline PET scan (PET subjects) or the first dose of trial medication (PBMC subjects).
15. Presence or history of drug or alcohol abuse, or intake of more than 14 units of alcohol weekly, within the 12 months before the baseline PET scan (PET subjects) or the first dose of trial medication (PBMC subjects).
16. Evidence of drug abuse on urine testing.
17. Regular consumption (eg ≥ 4 days/week) of excessive quantities of xanthine-containing beverages (eg ≥ 5 cups of coffee or the equivalent per day) within 30 days before screening, or between screening and the baseline PET scan (PET subjects) or the first dose of trial medication (PBMC-only subjects).
18. Receipt of an investigational product (including prescription medicines) or device within 3 months* before the baseline PET scan (PET subjects) or the first dose of trial medication (PBMC subjects); in the follow-up period of another clinical trial at the time of screening for this study.
*(or 5 half-lives, or twice the duration of the biological effect, of the investigational product – whichever is longer).
19. Use of the following:
 - a prescription medicine during the 28 days* before the baseline PET scan (PET subjects) or the first dose of trial medication (PBMC subjects);
 - an over-the-counter medicine, including vitamins, herbal, or dietary supplements (including St John's Wort), with the exception of acetaminophen (paracetamol), during the 7 days* (or 28 days if the medicine is a potential hepatic enzyme inducer) before the baseline PET scan (PET subjects) or the first dose of trial medication (PBMC subjects).

*(or 5 half-lives of the medicine – whichever is longer).

20. Loss of more than 400 mL blood during the 3 months before the trial, eg as a blood donor.
21. Alanine aminotransferase (ALT) or aspartate aminotransferase (AST) levels $\geq 1.5 \times$ upper limit of normal (ULN) at screening, or before the baseline PET scan (PET subjects), or before the first dose of trial medication. A repeat is allowed on one occasion for determination of eligibility.
22. QT value, measured at screening, or before the baseline PET scan (PET subjects) or first dose of trial medication (PBMC subjects), greater than 450 msec (men) or 470 msec (women), using Fridericia's formula (QTcF) for correction.
Triplicate measurements will be made, and a mean QTcF value higher than those stated will lead to exclusion. A repeat (in triplicate) is allowed on one occasion for determination of eligibility.
23. Family history of long QT syndrome or sudden death.
24. Clinically significant ECG abnormalities, as determined by the investigator or medical monitor, including (but not limited to):
 - abnormal ST-T-wave morphology or left ventricular hypertrophy.
 - PR (PQ) interval shortening < 120 msec (PR < 120 msec but > 110 msec is acceptable if there is no evidence of ventricular pre-excitation).
 - PR (PQ) interval prolongation (> 220 msec), intermittent second- (Wenckebach block while asleep or in deep rest is not exclusionary) or third-degree atrioventricular (AV) block.
 - Persistent or intermittent complete bundle branch block, incomplete bundle branch block, or intraventricular conduction delay with QRS > 120 msec.
25. Blood pressure and pulse rate in seated position at the screening examination outside the ranges: blood pressure 90–140 mm Hg systolic, 40–90 mm Hg diastolic; pulse rate 40–100 beats/min. The average of triplicate measurements (each 5 min apart) will be used to assess eligibility.
Repeat measurements are permitted if values are borderline (ie values that are within 5 mm Hg for blood pressure or 5 beats/min for pulse rate) or if requested by the investigator. Subjects can be included if the repeat value is within range or still borderline, but deemed not clinically significant by the investigator.
26. Significant ($> 10\%$) weight loss or gain within 30 days before the (first) screening visit or before the baseline PET scan (PET subjects) or first dose of trial medication (PBMC subjects).
27. Unsatisfactory venous access
28. Subjects with a COVID-19 vaccination within 2 weeks of screening, or who are due to receive a dose of a COVID-19 vaccine while participating in the study.

29. Positive test for hepatitis B, hepatitis C or human immunodeficiency virus (HIV).
30. Vegan, or unwilling to eat a high-fat breakfast including eggs and dairy (eg for personal or religious reasons).
31. Employed by, or a first-degree relative of an employee of, Asceneuron S.A. or a clinical trial site participating in this study.
32. Possibility that the volunteer will not cooperate with the requirements of the protocol.
33. Objection by general practitioner (GP) to volunteer entering trial.

The following exclusion criteria also apply to subjects who will be given PET scans during the study.

34. Significant structural brain abnormality, as determined by MRI.
35. Significant exposure to ionising radiation as part of research (defined as International Commission on Radiological Protection [ICRP]¹¹ category IIb or above: no more than 10 mSv in addition to natural background radiation including this trial), within the 12 months before the first dose of tracer.
36. Unsuitable or unwilling to undergo the imaging procedures, as determined by an MRI safety questionnaire. Reasons for exclusion include but are not limited to: presence of a cardiac pacemaker or other implanted electronic device; ferromagnetic metal foreign bodies, intracranial aneurysm clips or other metallic objects; non-MRI compatible heart valves; inner ear implants; or a history of claustrophobia.
37. Contraindication for arterial cannulation: Allen's test indicating potential risk in placement of the arterial cannula.

9.4 Withdrawal of subjects from the trial

9.4.1 *Subject withdrawal*

Subjects are free to withdraw from the trial at any time without giving reasons. Furthermore, the investigator may withdraw a subject for reasons such as intolerance to trial medication, intercurrent illness, need for medication which is contraindicated, significant non-compliance with the requirements of the trial, or withdrawal of consent. The investigator will assess the reasons for withdrawal as far as possible and will fully record the circumstances and medical details.

Subjects will be informed before they agree to take part in the trial that, if they withdraw or are withdrawn:

- the investigator will stop collecting information about them; and
- they can ask the investigator to destroy any identifiable samples taken from them.

The investigator will ask withdrawn subjects to consent to a follow-up examination, to check that they have come to no harm as a result of taking part in the trial.

Provided that the subject agrees, they will undergo, at withdrawal from the trial (or as soon as possible afterwards), the standard medical examination and laboratory tests which they would have undergone had they completed it. The investigator will record in the case report form (CRF) the results of the follow-up examination of withdrawn subjects, if they give their consent for that.

9.4.2 *Individual subject stopping criteria*

A subject who meets any of the following criteria will receive no further doses.

- SAE considered related to study treatment.
- ALT $\geq 3 \times$ ULN.
- Any condition that, in the judgment of the investigator or sponsor, might place the subject at risk or invalidate the trial.

Subjects who meet the above criteria will be considered discontinued from dosing. However, the investigator may ask the subject to continue their participation in the study, so they can be monitored for safety, PK and PD, or the investigator may withdraw the subject from the trial.

9.4.3 *Replacement of withdrawn subjects*

Withdrawn subjects will be replaced at the discretion of the sponsor and investigator. Replacements for withdrawn subjects will receive the treatment intended for the withdrawn subject, from the start of the trial.

For subjects withdrawn because of AEs considered possibly related to study treatment (see section 14.2), possible replacement will be discussed by mutual agreement between sponsor and investigator.

10 *Treatments*

10.1 *Treatments administered*

All subjects

All subjects will receive once-daily doses of ASN51 for 14 days (see section 8.1).

All doses will be given orally, in the fasted or fed state, with about 240 mL of water. Extra water can be given if a subject has trouble swallowing the tablets; that will be recorded in source documents.

Fasting requirements are described in section 11.

PET subjects

PET subjects will also receive IV doses of the radiolabelled tracer [¹⁸F]-IMA601 (non-IMP) on up to 3 occasions (1 at each imaging session).

If one or both on-treatment PET scans need to be rescheduled, eg owing to a technical failure, subjects may have additional imaging sessions. However, subjects will receive no more than 3 doses of [¹⁸F]-IMA601 during the study.

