12.3 Follow-up

Subjects will return to the ward 9–11 days after their final dose of trial medication, or 2–4 days after imaging session 3 (whichever is later; PET subjects only) for a follow-up visit. Withdrawn subjects who consent to a follow-up visit will undergo the same procedures (see section 9.4).

The follow-up period may be extended if:

1. a subject has an unresolved AE at the follow-up visit, which, in the opinion of the investigator, merits further follow-up;
2. plasma concentrations of IMP were higher than predicted, and/or the half-life of the IMP was very long, and the investigator considers that additional follow-up is necessary; or
3. new information becomes available that supports an extended follow-up period.

The investigator will decide on the nature of the follow-up. For example, subjects may have a telephone follow-up at which they are asked about AEs, or subjects may be asked to attend extra outpatient visits for additional monitoring of blood levels or effects of IMP, and for extra safety tests. The extra safety tests might include tests that are not described in this protocol. The investigator reserves the right, during or after the study, to repeat safety tests or to do any extra safety tests that are in the best interest of the subjects.

If a subject has an SAE during the study, they will also have an additional follow-up by telephone at 28 days (± 3) days after their final dose of trial medication.

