14.3 Procedures for dealing with serious adverse events

In the event of any SAE which, in the investigator’s opinion, justifies termination or modification of the trial (see section 8.4), dosing will be stopped and the sponsor’s medical monitor will be informed immediately (within 24 h of the investigator becoming aware of the event) by telephone or email, as follows.

Medical monitor: [REDACTED] MD

Tel: [REDACTED]

Mobile: [REDACTED]

Email: [REDACTED]

All SAEs occurring after the signing of the ICF until the follow up visit, regardless of study drug relationship, must be reported to the sponsor’s pharmacovigilance

department, with as much information as possible, within 24 h of the investigator becoming aware of the event. The investigator will complete an SAE form and provide it to the sponsor's pharmacovigilance department, via the following contact details.

Monitor: [REDACTED] MD

Tel: [REDACTED]

Mobile: [REDACTED]

Email: [REDACTED]

The sponsor will also be notified by email [REDACTED]
[REDACTED]

The investigator will notify the REC of SAEs that occur during this trial, if applicable, in accordance with the SOPs issued by the Research Ethics Service (RES)²³.

The sponsor is responsible for determining the expectedness of the event, using the reference safety information in the IB¹. The sponsor will notify the MHRA of all suspected unexpected serious adverse reactions (SUSARs), and will be responsible for ensuring that the REC is notified of SUSARs, if applicable. SUSARs that are fatal or life-threatening must be notified to the MHRA and REC within 7 days after the sponsor has learned of them. Other SUSARs must be reported to the REC and MHRA within 15 days after the sponsor has learned of them.

If a subject has an SAE during the study, they will have an additional telephone follow-up as described in section 12.3.

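### Protocol 9.4.1 ends information collection for subjects the investigator withdraws as well as those who revoke consent, which conflicts with the SAE duties in 14.3 and 12.3

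*Protocol*

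**What the plan says.** Protocol 9.4.1 introduces the rule with "Subjects will be informed before they agree to take part in the trial that, if they withdraw or are withdrawn", and the first consequence it lists is that "the investigator will stop collecting information about them". Both routes out of the trial are covered. The same section gives the investigator's route: "the investigator may withdraw a subject for reasons such as intolerance to trial medication, intercurrent illness" are among the reasons. Section 9.4.2 adds that a subject who meets an individual stopping criterion may either stay in the trial for monitoring or be withdrawn from it.

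The section also contains a safeguard: "The investigator will ask withdrawn subjects to consent to a follow-up examination, to check that they have come to no harm". If the subject agrees, they have "at withdrawal from the trial (or as soon as possible afterwards), the standard medical examination and laboratory tests" they would have had on completing the trial, and the results go in the CRF with consent. Sections 14.4 and 17 repeat this. Section 17 also lets the subject keep the results out of the eCRF. Section 12.3 says "Withdrawn subjects who consent to a follow-up visit will undergo the same procedures (see section 9.4").

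Other sections set safety end dates without mentioning withdrawn subjects. Section 14.3 makes reportable "All SAEs occurring after the signing of the ICF until the follow up visit, regardless of study drug relationship". Section 12.3 requires a telephone follow-up at 28 (±3) days after the final dose for any subject with an SAE, and 14.3 points to it.

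For a Group 1 subject withdrawn before Day 20, section 8.5.1 says that "all available safety, tolerability, and PK data from that subject will be included in the SRG review". SAP 12.1 keeps withdrawn subjects in the analyses and does not impute missing data.

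**The concern.** A subject removed for a safety reason is treated as if they had revoked consent. These are the subjects in whom a further related event is of most interest, and the protocol's own figures imply that the drug persists for days after the last dose.

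A site cannot both stop collecting information on such a subject and meet the SAE duties in 14.3 and 12.3. If it follows 9.4.1, a later event may never be recorded. Three uses of the data depend on what was recorded:

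- the trial stopping rule in 8.4.1, whose first limb is met by one SAE at least possibly related to treatment;
- the SRG decision on opening Group 2, which sees only the data available from withdrawn subjects;
- the AE tables, where a withdrawn subject stays in the denominator while later events are absent.

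No planned output would show the truncation directly. The withdrawal listing (SAP Listing 16.2.1.2) gives the date, study day and reason for withdrawal, but not when safety information ended.

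**Working it through.** The plan gives no figure to reproduce on this point, so the main check is a comparison of passages.

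**1. When safety information ends for a subject withdrawn by the investigator**

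- 9.4.1: at withdrawal, apart from one consented examination then or soon afterwards.
- 14.3: SAEs to the follow-up visit. If the subject declines any visit, the end of this window is undefined.
- 12.3, SAE call: 28 (±3) days after the final dose, with no condition about withdrawal.
- 12.3, follow-up visit: depends on consent and refers to 9.4. This part is consistent with 9.4.1, although its paragraph opens with a visit 9–11 days after the final dose, so the timing for withdrawn subjects is unclear.
- Protocol section 12: AEs recorded to the subject's last visit, which for a withdrawn subject may be the withdrawal examination.

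The direct conflicts are therefore the SAE window in 14.3 and the SAE call in 12.3.

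**2. Length of the gap**

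A completer's last dose is on Day 14. Follow-up is Day 14 + 9 to 14 + 11 = Days 23–25, the SRG data run to Day 14 + 6 = Day 20, and the SAE call is at Day 14 + 28 = 42 (±3). If a subject is withdrawn and examined on the day of the last dose, the 9–11 days to the normal follow-up time are exposed.

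**3. Which events could be lost**

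- A subject stopped under the first criterion in 9.4.2 has a related SAE, and 8.4.1 limb 1 is already met. Later events cannot change that decision.
- A subject withdrawn for a related, non-serious AE has not met limb 1. Under 14.1 an AE leading to withdrawal of drug treatment is normally significant, so it may count as one of the two events in limb 2. A later SAE (limb 1) or a second qualifying AE (limb 2) could then be decisive.

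**4. Exposure remaining when collection ends (illustration)**

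Protocol 6.7 equates 6 days with 3 half-lives, so the half-life is about 144 h / 3 = 48 h. Assume linear one-compartment kinetics and collection ending 24 h after dose k. With r = 2^(−24/48) = 0.707 per day, the share of total exposure still to come is (r + r² + … + r^k)/k. At 9 days after the last dose it is that share times r^8 = 0.0625.

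| Doses taken | Remaining at 24 h | Remaining at 9 days |
|---|---|---|
| 1 | 0.707 | 0.044 |
| 5 | 0.397 | 0.025 |
| 7 | 0.314 | 0.020 |
| 14 | 0.171 | 0.011 |

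This is exposure after the assumed cut-off, not the probability of an event.

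**5. Stopping rule, upper bound**

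Section 8.5.1 needs at least 4 evaluable subjects from a group of up to 6, so 2 of 6 may be withdrawn. If nothing at all were counted from those 2, the chance of seeing at least one related SAE in the group falls from 1 − (1 − p)^6 to 1 − (1 − p)^4. The per-subject rates p are assumed, because the documents give none.

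| p | 6 counted | 4 counted |
|---|---|---|
| 2% | 0.114 | 0.078 |
| 5% | 0.265 | 0.185 |
| 10% | 0.469 | 0.344 |
| 20% | 0.738 | 0.590 |

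The real loss is smaller, because events before withdrawal and those found at a consented examination still count.

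**The case against.** The strongest reply is that the passages can be read together. Under 14.3 the 24-hour clock starts when the investigator becomes aware of the SAE. Active collection could end at withdrawal while any SAE that becomes known is still reported, and the SRG receives whatever is available. Every withdrawn subject is also asked to accept a follow-up examination, 9.4.2 lets the investigator stop dosing without ending participation, and 12.3 allows extended follow-up for an unresolved AE at the follow-up visit. Both earlier clinical studies of ASN51 had no SAEs and only mild or moderate treatment-emergent events (Protocol 6.2.2).

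Much of this stands. A reader might infer that nothing is collected after any withdrawal. The documents do not support that, given the consented examination in 9.4.1, 12.3, 14.4 and section 17. A reader might also infer that 9.4.1 and 12.3 contradict each other on the date of that examination. Since 12.3 defers to 9.4, this is at most an ambiguity.

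The reply does not remove the conflict. An SAE that nobody asks about may never become known. The examination needs further consent, its results can be kept out of the eCRF, and if it is done at withdrawal it cannot record later events. Staying in the trial under 9.4.2 is discretionary. The SAE call in 12.3 is itself a planned contact, so reporting on awareness does not reconcile it with a stop on collection.

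**Conclusion.** The conflict is real but limited. Section 9.4.1 stops collection for subjects withdrawn by the investigator, while 14.3 and the SAE call in 12.3 carry no matching exception. What remains exposed is AEs and SAEs arising after the withdrawal examination, or in subjects who decline it.

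The size of the loss cannot be estimated from the documents. It matters mainly because the numbers are small: one subject is 1 of 6 (17%) of a full group, and one possibly related SAE meets the first limb of the stopping rule. The 17–71% of exposure remaining 24 h after the last dose rests on a 48 h half-life, one-compartment kinetics and an assumed cut-off. It shows that drug is still present and is not an event risk. The binomial figures rest on assumed rates and on two subjects contributing nothing.

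It would be tempting to conclude that the AE summaries are biased by a known amount, or that any missed event would change the stopping decision. Neither follows. No event rate is given, and where a related SAE led to the withdrawal the rule has already been met. The consent form was not available, so what subjects actually agree to about later data could not be checked.

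**What to change.** Reconcile the passages as follows.

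- In 9.4.1, limit the stop on collecting information to subjects who withdraw consent.
- State that for subjects withdrawn by the investigator, AE and SAE information continues to be collected to the end dates already set in 12.3 and 14.3, and word the consent form to match.
- In 12.3, say whether a withdrawn subject's examination takes place at withdrawal or at the visit 9–11 days after the final dose, and use the same timing in 9.4.1 and 14.4.
- Show the last date of safety information for each withdrawn subject in the SRG review and as a column in SAP Listing 16.2.1.2. Listing 16.2.1.1 already carries a follow-up date, so part of this exists.

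The cost is minor protocol and consent-form wording and one listing column. Subjects who withdraw consent are unaffected, and no new type of assessment is needed.
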